“Early Sodium Intake in Preterm Newborns; Randomized Clinical Trial”

NCT04035564

January 2018

Introduction

Hyponatremia is a common complication among preterm infants, renal losses of sodium contribute to the development of hyponatremia in preterm newborns. Sodium imbalances impact in newborns outcome. There is controversy about the time of initiation and the requirements of sodium in premature infants. Hypothesis: early (24 hours of life) sodium supplementation (5mEq/kg/day) prevents the develop of hyponatremia in preterm infants.

This study is a randomized controlled trial in infants less than 35 weeks gestation admitted to the Newborn Intensive Care Unit at Children Hospital in Saltillo Coahuila Mexico.

Infants receive at 24 hours of life; sodium (5mEq/kg/day) versus less than 1mEq/kg/day. Weight, serum and urine sodium, serum chloride, serum and urine creatinine, serum chloride, bicarbonate and glucose are monitored daily during the first 3 days of life. Patients are assessed for hyponatremia, hypernatremia, weight change, sepsis, necrotizing enterocolitis and intraventricular hemorrhage.

Objectives:

1. Compare the risk of hyponatremia in the first 72hrs of life, in preterm newborns with early sodium intake and late sodium intake.
2. Compare the risk of hypernatremia in the first 72hrs of life, in preterm newborns with early sodium intake and late sodium intake.
3. Assess the change in serum sodium in preterm newborns with early sodium intake and late sodium intake.
4. Assess the weight change in preterm newborns with early sodium intake and late sodium intake.
5. Assess the development of complications (sepsis, necrotizing enterocolitis, intraventricular hemorrhage, mortality) in preterm newborns with early sodium intake and late sodium intake.

Study design and statistical analysis

This study is a randomized controlled trial.

Eligibility criteria:

Preterm infants <35 weeks of gestation.

Less than 24 hours of life.

Exclusion criteria:

Urinary malformations
Congenital abdominal wall defect
Intestinal atresia / obstruction
Congenital heart defect

The eligible patients will be simple randomized in two groups:

1. Comparison: Sodium administration, enteral and/or parenteral less than 1mEq/kg/day starting on day of life one.
2. Intervention: Sodium administration, enteral and/or parenteral of 5mEq/kg/day starting on day of life one.

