At admission, gestational age and sex and birth weight will be recorded. Weight will be evaluated every 24 hours for 3 days.

Blood samples will be taken every 24 hours for 3 days to assess serum sodium, creatinine, glucose, sodium bicarbonate and serum chloride levels.

Urine samples will be taken every 24 hours for 3 days to assess urine sodium and urine creatinine levels.

The incidence of hyponatremia, hypernatremia, change of serum sodium and weight change will be evaluated and compared between groups during this time frame (72hrs).

The patients will be following through hospital stay to record the development of sepsis, necrotizing enterocolitis, intraventricular hemorrhage and mortality.

The distribution of variables will be assessed with Shapiro Wilk test, normally distributed data will be compared with t test or Chi squared test and those with abnormal distribution with Mann-Whitney U test or Fisher exact test. The risk of hyponatremia and hypernatremia will be expressed using relative risk.

The change of serum sodium, creatinine, chloride, sodium bicarbonate, glucose levels and weight will be evaluated using repeated measures ANOVA or Kruskal-Wallis test depending on data distribution.

Exploratory analysis will include sodium balance (according to sodium intake and urinary excretion), urine output and total fluid administration.

IBM SPSS Statistics (IBM Corp. Released in 2013. IBM Statistics for Windows, Version 21.0. Armonk NY: IBM Corp.) will be used for statistical analysis. A p-value <0.05 will be considered statistically significant.

Definitions:

Hyponatremia: Serum sodium <130mEq/L

Hypernatremia: Serum sodium >150mEq/L

Change in serum sodium: The difference between serum sodium (at 48 and 72hrs) and initial serum sodium.

Weight change: The difference between weight (at 24, 48 and 72hrs) and birth weight.

Sepsis: Positive blood culture and/or 5 days of continuous antimicrobial therapy.

Necrotizing enterocolitis: Necrotizing enterocolitis according to Bell staging (II or grater).

Intraventricular hemorrhage: Bleeding into the brain's ventricular system (intracranial ultrasound).

Mortality: Death during hospitalization.

References

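### The hyponatremia comparison is planned without adjustment for gestational age, a baseline value already recorded; the crude analysis is valid but gives up some power.

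*Combined protocol and SAP*

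**What the plan says.** The Introduction states one hypothesis: early sodium "prevents the develop of hyponatremia in preterm infants". Objective 1 compares the risk of hyponatremia over the first 72 hours of life, and objective 2 does the same for hypernatremia. The Definitions set the cut-offs at below 130 and above 150 mEq/L.

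Under Study design and statistical analysis, the tests are given in one sentence: "normally distributed data will be compared with t test or Chi squared test and those with abnormal distribution with Mann-Whitney U test or Fisher exact". For the two sodium outcomes, "The risk of hyponatremia and hypernatremia will be expressed using relative risk". The significance rule is "A p-value <0.05 will be considered statistically significant". No covariate, adjusted model or stratification factor is named for any yes/no outcome, and allocation is by simple randomization to two groups.

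On baseline data the plan says: "At admission, gestational age and sex and birth weight will be recorded". Blood is drawn every 24 hours for 3 days. A starting sodium value is mentioned only in the Definitions, where change in serum sodium is "The difference between serum sodium (at 48 and 72hrs) and initial serum sodium". That value is given no time. The start of sodium is described in the Introduction as 24 hours of life, and in the two group descriptions as day of life one.

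**The concern.** Eligibility has an upper limit of 35 weeks and no lower one, so maturity may vary widely between infants. The Introduction itself attributes hyponatremia partly to renal sodium losses, so it is reasonable to expect gestational age to predict who falls below 130 mEq/L. A crude two-by-two comparison leaves that predictable variation in the error term. Because randomization is simple and unstratified, the arms can also differ in gestational age by chance, and a crude relative risk carries any such difference.

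At stake is power for the one hypothesis the trial states. With no sample size or power calculation in the documents, adequate power cannot be assumed. Naming the covariate in advance also prevents its being chosen after the results are seen.

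**Working it through.** The plan gives no figure to reproduce. What follows is illustrative, and every rate and correlation in it is an assumption.

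**Inputs.** From the documents: significance level 0.05 (two-sided assumed), two arms (1:1 assumed), and a yes/no event defined by a cut-off of serum sodium. Assumed: 25% versus 10% hyponatremia; 50, 75 or 100 infants per arm; correlation of 0.3 or 0.5 between a baseline covariate and the later sodium value.

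**Step 1, crude power.** With p1 = 0.25, p2 = 0.10 and mean 0.175:

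power = Φ{[(p1 − p2) − 1.96·√(2·0.175·0.825/n)] / √[(p1(1−p1) + p2(1−p2))/n]}

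At n = 50: (0.15 − 1.96 × 0.0760)/0.0745 = 0.014, which gives 50.6%. The same formula gives 68.0% at 75 per arm and 80.2% at 100.

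**Step 2, what a covariate explains once sodium is cut at 130.** Treat later sodium as normal, with share r² explained by the covariate. For an event rate p, the share explained in the yes/no outcome is

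R² = Var[Φ((Φ⁻¹(p) − r·x)/√(1 − r²))] / [p(1 − p)]

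- r² = 0.10 (r about 0.3): R² is 0.037 at p = 10% and 0.051 at 20%; take 0.04.
- r² = 0.25 (r = 0.5): R² is 0.104 at 10% and 0.134 at 20%; take 0.12.
- r² = 0.25 + 0.3² = 0.34 (a second independent covariate at 0.3): interpolating between the values at 0.25 and 0.40 (0.185 at 10%, 0.226 at 20%) gives 0.153 and 0.189; take 0.17.

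Cutting the outcome therefore removes about half or more of the gain available for continuous sodium.

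**Step 3, adjusted power.** Replace n by n/(1 − R²) in Step 1:

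| Per arm | Crude | r = 0.3 (R² 0.04) | r = 0.5 (R² 0.12) | r = 0.5 plus second at 0.3 (R² 0.17) |
|---|---|---|---|---|
| 50 | 50.6% | 52.2% | 55.8% | 58.4% |
| 75 | 68.0% | 69.8% | 73.6% | 76.0% |
| 100 | 80.2% | 81.8% | 85.0% | 87.0% |

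The gains are about 2, 5 and 7 to 8 points.

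**Step 4, simulation.** Comparing the Chi-squared test with a standardised logistic analysis at the same rates gave gains of about 2 points at 0.3, 5 to 7 at 0.5, and 6 to 9 with the second covariate. With gestational age as the only covariate, the gains were 1 to 3 points at correlation 0.3 and 5 to 6 at 0.5. At 30% versus 15% with r² = 0.25, power rose from 52% to 58% at 60 per arm and from 79% to 85% at 118 per arm.

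**Step 5, type I error.** With equal risks in both arms and 30 infants per arm, one set of runs at a 30% event rate gave 5.3% to 7.2% for the adjusted tests, against 4.6% to 5.7% for Chi-squared. Other null runs at that size reached 8.1%, and at 20 per arm 8.1% to 10.0%. At 118 per arm the adjusted tests stayed at 4.9% to 5.4%. Part of any apparent small-sample gain is therefore inflated test size.

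**The case against.** The strongest reply is that nothing here is wrong. The Chi-squared test, Fisher's test and the crude relative risk are all valid under randomization, and chance imbalance is already allowed for in the test's error rate. The gain rests on a correlation the documents do not supply: it is a few points in the middle of the assumed range and nil if the covariate predicts nothing. The missing sample size is a more basic gap. All of this stands, and it is why the point is one of efficiency. It does not remove the case for prespecifying a covariate that is already collected.

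A reader might also infer something stronger: that a baseline serum sodium exists for every infant, and that ignoring it wastes power at no cost. The documents do not support this, for three reasons.

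- Only gestational age, sex and birth weight are listed at admission. Initial serum sodium is undated. Change is taken at 48 and 72 hours only, whereas weight change also uses 24 hours, so the initial value may be the 24-hour sample. With sodium starting either at 24 hours of life or on day of life one, that sample could follow the start of treatment, and adjusting for it could then remove part of the effect.
- Nothing excludes the initial sample from the 72-hour event window. If it counts, the covariate partly defines the outcome.
- Adjustment is not free in a small trial, as the null runs show, and the trial's size is not stated.

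**Conclusion.** The point holds as an efficiency and chance-imbalance matter for objective 1. The planned comparison is crude, although a clearly pre-treatment and plausibly prognostic variable, gestational age, is on record.

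The size is modest and conditional. At 25% versus 10% and 50 to 100 per arm, adjustment adds about 2 points of power at a correlation of 0.3, about 5 to 7 at 0.5, and about 6 to 9 when a second independent covariate at 0.3 is added to one at 0.5. None of these inputs comes from the documents. If gestational age is the only usable covariate, the single-covariate figures apply.

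It would be wrong to conclude that the crude relative risk is biased or that its test is invalid. Nor do the documents establish initial serum sodium as a usable baseline covariate.

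**What to change.** Prespecify the main analysis of objective 1 as a logistic model with arm and gestational age (continuous), standardised over all infants to give an adjusted relative risk and risk difference with 95% intervals. Keep the crude relative risk as a supporting result.

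Use a small-sample-corrected standard error or a permutation test. State a minimum number of events for hyponatremia and for hypernatremia (for example 10 in total, an illustrative figure to be checked at the planned size), below which the planned crude or exact test is used. Apply the same model to hypernatremia where that minimum is met.

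Reconcile the statements on sampling time and on the start of sodium. Add initial serum sodium as a covariate only if the protocol then defines it as drawn before the allocated sodium starts and does not count that sample as an event.

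The cost is a few sentences of analysis text and a slightly more complex model, with no new infants and no new data for gestational age. The downside is possible instability, or type I error above 5%, when infants or events are few; the corrected test and the fallback rule are there for that reason.

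### Serum sodium change and weight change are compared without baseline as a covariate, so objectives 3 and 4 may lose precision that a cheap adjustment could recover.

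*Combined protocol and SAP*

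**What the plan says.** Objectives 3 and 4 are to "Assess the change in serum sodium in preterm newborns with early sodium intake and late sodium intake" and to "Assess the weight change in preterm newborns with early sodium intake and late sodium intake".

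The Definitions give both outcomes as subtractions: "Change in serum sodium: The difference between serum sodium (at 48 and 72hrs) and initial serum sodium" and "Weight change: The difference between weight (at 24, 48 and 72hrs) and birth weight". No unit is given for weight change.

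Under Study design and statistical analysis, the test is repeated measures ANOVA, or Kruskal-Wallis if the distribution calls for it: "The change of serum sodium, creatinine, chloride, sodium bicarbonate, glucose levels and weight will be evaluated using repeated measures ANOVA". The text does not say whether the ANOVA runs on the differences or on the raw serial values. No ANCOVA, regression or other adjustment appears anywhere.

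The variables that could serve as covariates are already in the plan: "At admission, gestational age and sex and birth weight will be recorded", and "Blood samples will be taken every 24 hours for 3 days to assess serum sodium". Allocation is unstratified: "The eligible patients will be simple randomized in two groups".

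**The concern.** Baseline enters only by subtraction, or as one level of the time factor if raw values are analysed. In the second case the group-by-time contrast is still a comparison of change scores. Either way the coefficient on baseline is fixed at 1 instead of being estimated. Where the true coefficient is well below 1, subtraction adds baseline noise to the outcome, and the arm difference is estimated less precisely than the same data allow.

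At stake is the chance of detecting an arm difference in serum sodium or weight over 72 hours.

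**Working it through.** **Inputs.** The documents give no sample size, SD, correlation or expected effect, so there is no planned figure to reproduce. Assumed below: 1:1 allocation, two-sided 0.05, N = 30 to 100 in total. Write ρ for the baseline-to-follow-up correlation and s for the later SD divided by the initial SD.

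**Sodium, one time point** (in units of the initial variance):
- Change score: 1 + s² − 2ρs
- ANCOVA on baseline: s²(1 − ρ²)
- The difference between them is (1 − ρs)², so the proportional cut is (1 − ρs)² / (1 + s² − 2ρs).

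With equal SDs (s = 1) the cut is (1 − ρ)/2:

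| ρ | 0.3 | 0.5 | 0.7 | 0.9 |
|---|---|---|---|---|
| Cut | 35% | 25% | 15% | 5% |

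With ρ = 0.5 and unequal SDs:

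| s | Calculation | Cut |
|---|---|---|
| 0.8 | 0.36 / 0.84 | 43% |
| 1 | 0.25 / 1 | 25% |
| 1.25 | 0.1406 / 1.3125 | 11% |
| 1.5 | 0.0625 / 1.75 | 4% |
| 2 | 0 / 3 | 0% |

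The gain vanishes where ρs = 1.

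**Sodium, mean of 48 and 72 hours.** With equal SDs and equal correlations the cut is 2(1 − ρ)/3, which is 47%, 33%, 20% and 7% for the same four values of ρ.

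**Power.** Simulated for an effect of 0.5 follow-up SD at one time point, ρ = 0.5:
- Equal SDs: about 47% (change score) against 58% (ANCOVA) at N = 60, and 69% against 80% at N = 100.
- s = 1.5: 56% against 58% at N = 60, and 81% against 81% at N = 100.

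**Cost of one covariate.** The variance factor is about 1 + 1/(N − 4): 1.04 at N = 30, 1.02 at N = 60, 1.01 at N = 100.

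**Weight in grams, birth weight as covariate.** Illustrative inputs: birth weight uniform from 700 to 2300 g (mean 1500, variance 1600²/12 = 213,333), mean loss 7% (arms at 8% and 6%), scatter SD 4 percentage points.
- Residual variance: 0.04² × (1500² + 213,333) = 3,941.
- *Percent loss unrelated to birth weight.* Variance explained by birth weight is 0.07² × 213,333 = 1,045. The cut is 1,045 / (1,045 + 3,941) = 21%, or 20% at N = 60 after the covariate cost (0.79 × 1.018 = 0.80). At a mean loss of 8% the figures are 26% and 24%. These agree with a range of about 18% to 26% for such settings at N = 60.
- *Percent loss 4 points higher per 1000 g lower birth weight.* The slope of grams lost on birth weight at the mean is 0.07 − 0.00004 × 1500 = 0.01. That explains 0.01² × 213,333 = 21, about 0.5%, which is less than the 1.8% cost. The result is a net loss of about 1%.
- *Narrower spread* (mean 1600 g, SD 300 g, scatter 5 points, percent loss unrelated to birth weight). Explained 0.07² × 300² = 441; residual 0.05² × (1600² + 300²) = 6,625. The cut is 441 / 7,066 = 6% before the covariate cost.

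**Is the initial sodium pre-treatment?** Its time is not stated. Sodium change is defined only at 48 and 72 hours, while weight change is also defined at 24 hours, which suggests that the initial sample is the one near 24 hours. The Introduction starts study sodium 24 hours after birth; the arm descriptions start it on the first day of life. These may be two ways of counting. A pre-treatment sample is plausible but not established.

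**The case against.** The strongest reply is that an unadjusted change-score comparison is valid in a randomised trial, and that the gain is speculative. The sodium gain depends on the SD ratio as much as on the correlation, and the plan gives neither. At ρ = 0.5 and an SD ratio of 2 the gain is nil. The weight gain depends on how percent loss varies with birth weight and on how widely birth weights are spread. The hypothesis concerns hyponatremia, which this does not touch. The planned test may also be a group-by-time interaction with several degrees of freedom, or Kruskal-Wallis; the figures above describe neither exactly.

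Most of this stands, and it limits the size and priority of the point. It does not remove the point: in large samples a baseline covariate cannot do worse than subtraction, and in small ones the penalty is a few percent.

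A reader might infer more from simple randomisation and the missing covariates, namely that the plan is biased or inflates the type I error. The documents do not support that. Chance imbalance is part of what the unadjusted standard error measures. A reader might also infer that grams adjusted for birth weight can only help. That is true only in large samples; at N = 60 it can lose about 1%.

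**Conclusion.** The point holds as a modest efficiency improvement for objectives 3 and 4. Baseline is not a covariate under any reading of the plan.

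For sodium, the recoverable variance at one time point is 5% to 35% with equal SDs. At ρ = 0.5 it is anywhere from 0% to 43% across SD ratios of 0.8 to 2. It is available only if the initial sample precedes study sodium.

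For weight in grams it ranges from about a quarter down to nothing, or a loss of about 1%. It is larger when birth weights vary widely and percent loss is similar across them.

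All sizes are assumptions, because the plan supplies no inputs. It would go too far to read the missing adjustment as weakening the hyponatremia or hypernatremia comparisons: those are relative risks from a separate analysis. Using Kruskal-Wallis on repeated daily values is a different question, not judged here.

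**What to change.** 1. Analyse serum sodium at 48 and 72 hours by ANCOVA or a mixed model with arm, time, arm-by-time and initial sodium. Define initial sodium as a sample taken before study sodium starts.
2. State that weight is analysed in grams, and analyse it at 24, 48 and 72 hours by the same kind of model with birth weight as the covariate.
3. Gestational age may be added, but little should be expected from it. In simulation with assumed correlations of 0.2 with initial and 0.3 with later sodium, it added 0 to 4 points of power once initial sodium was in the model.
4. Reconcile the two statements of when study sodium starts, in the Introduction and in the arm descriptions, so that the pre-treatment sample can be identified. If there is none, the sodium gain is lost and only the weight adjustment applies.
5. Leave the analysis of objectives 1 and 2 as planned.

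The cost is a few lines of SAP text on variables already collected, and about one degree of freedom per covariate (roughly 1% of variance at N = 100, 4% at N = 30). The downside is little or no gain in some settings.

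### Where repeated measures ANOVA is used, an infant missing one scheduled value is dropped from that outcome's model, including a 48 h change that was observed

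*Combined protocol and SAP*

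**What the plan says.** The section on study design and statistical analysis sets the schedule: "Blood samples will be taken every 24 hours for 3 days" and "Weight will be evaluated every 24 hours for 3 days". For these serial measurements it states "The change of serum sodium, creatinine, chloride, sodium bicarbonate, glucose levels and weight will be evaluated using repeated measures ANOVA", and the sentence goes on to allow Kruskal-Wallis instead, so the full choice is "repeated measures ANOVA or Kruskal-Wallis test depending on data distribution". The software is SPSS ("IBM Statistics for Windows, Version 21.0"); no procedure within it is named.

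The definitions fix the time points. Change in serum sodium is "The difference between serum sodium (at 48 and 72hrs) and initial serum sodium". Weight change is "The difference between weight (at 24, 48 and 72hrs) and birth weight". Birth weight is recorded at admission. Death is a recorded outcome: "Mortality: Death during hospitalization".

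The document has no analysis population, no missing-data rule, no provision for death or other loss before 72 h, and no mixed model or imputation. Transfer is not mentioned.

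**The concern.** Classical repeated measures ANOVA works on one complete row per infant. The usual SPSS routine of that name deletes a row if any time point is empty. An infant with an initial and a 48 h sodium has an observed value of an outcome that the plan defines, yet a missing 72 h sample would remove it. The 48 h result would then depend on a later event.

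At stake are objectives 3 and 4. On this branch they are answered by the infants who were fully measured to 72 h, not by all randomised infants with usable data. Values already collected are discarded, and if the reasons for loss differ by arm, the comparison loses part of the protection of randomisation. Some gaps are plausible: infants under 35 weeks with no lower gestational limit, daily blood sampling, and mortality as an outcome. How many gaps there will be is not documented.

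**Working it through.** The plan states no sample size, SD, missingness rate or death rate, so there is no figure of its own to reproduce. The check covers the mechanism and then the size under stated assumptions.

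**Inputs from the document**
- Sodium: 3 values needed (initial, 48 h, 72 h), from the definition of sodium change.
- Weight: 4 values used (birth, 24 h, 48 h, 72 h), from the definition of weight change. Birth weight is recorded at admission, so 3 can realistically be missing.

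**Assumption:** a chance p = 3%, 5% or 10% that a value is missing.

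**1. Mechanism.** A classical repeated measures ANOVA routine (in a package other than SPSS) ran on 20 complete subjects with three time points. With one 72 h value removed it refused the data as unbalanced. The infant must be dropped or the gap filled, and the plan provides no way to fill it.

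**2. Infants dropped, and the effect on precision.**
- Independent gaps in three values: share dropped = 1 − (1 − p)³.
- Monotone loss after the initial sodium (once lost, always lost, at rate p per interval): share dropped = 1 − (1 − p)².
- Standard error (SE) is taken as proportional to 1/√n. Against fully complete data, the complete-case SE is larger by the factor 1/√((1 − p)³).
- For the 48 h sodium change, the fairer comparator is every infant with both the initial and the 48 h value. That share is (1 − p)², against (1 − p)³ for complete rows, so the SE ratio is 1/√(1 − p). Under monotone loss the shares are (1 − p) and (1 − p)², which gives the same ratio.

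| p | Dropped, independent gaps (sodium; same for weight) | Dropped, monotone loss (sodium) | SE against complete data (independent gaps) | SE at 48 h against all available pairs |
|---|---|---|---|---|
| 3% | 1 − 0.97³ = 8.7% | 1 − 0.97² = 5.9% | 1.047 | 1.015 |
| 5% | 1 − 0.95³ = 14.3% | 1 − 0.95² = 9.8% | 1.080 | 1.026 |
| 10% | 1 − 0.90³ = 27.1% | 1 − 0.90² = 19.0% | 1.171 | 1.054 |

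The last column is the avoidable part at 48 h. No method restores values that were never measured.

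**3. Observed sodium values thrown away.** With independent gaps, a share (1 − p) of values is observed and (1 − p)³ is kept. The discarded share of observed values is therefore 1 − (1 − p)² = 5.9%, 9.8% or 19.0%.

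**4. Bias in the 48 h difference.** All simulations assume a true arm difference of 3.0 mEq/L.
- SD 5, correlation 0.6, loss of 20–40% if 48 h sodium is below 130 and 5% otherwise, same rule in both arms, 400,000 infants per arm: complete-case difference 2.88–2.94. The 72 h difference was essentially unbiased.
- Between-infant SD 3, residual SD 2.5, 200 infants per arm, loss of 10%, 30% or 50% if 48 h sodium is below 133 and 3% otherwise, same rule in both arms: complete-case 2.98, 2.91, 2.84, against 3.01, 3.00, 3.02 from all available 48 h values.
- SD 5, correlation 0.6 and assumed arm means, with loss of 20% or 40% tied to low sodium in the comparison arm and to sodium above 145 in the intervention arm: 2.86 and 2.67. The larger shortfall is (3.0 − 2.67)/3.0 = 11%. The 72 h difference stayed near 3.0.

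**The case against.** Several points on the other side stand.

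- **Only one branch is affected.** The plan does not rank ANOVA above Kruskal-Wallis. Applied time point by time point, Kruskal-Wallis would keep an observed 48 h value. A reader might infer that every serial analysis drops incomplete infants; the text does not support that. It does mean that the infants analysed could change with the outcome of a normality test, which is a reason to settle on one model.
- **A separate 48 h comparison is a possible reading.** The plan also says that the changes are compared between groups and names the t test and Mann-Whitney test for general comparisons. That leaves an ambiguity. The sentence written specifically for change over time, however, names repeated measures ANOVA.
- **Sodium and weight are separate outcomes.** It is tempting to say that one missed sample removes an infant from objectives 3 and 4 together. It does not: a failed blood sample leaves the weight data complete.
- **Larger weight losses are not justified.** Counting four values that can go missing gives 1 − (1 − p)⁴ = 11.5%, 18.5% and 34.4%, but this treats birth weight as often missing although it is recorded at admission.
- **Early loss is assumed.** Mortality is counted over the whole hospital stay, not to 72 h, and the measurement window is three days in one unit. If nearly all infants are fully measured, the issue almost vanishes.
- **The SPSS procedure is not named.** If a mixed model was intended, one sentence resolves the point. As written, the method's name ordinarily denotes the listwise routine.

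**Conclusion.** The point holds for the repeated measures ANOVA branch, outcome by outcome. Depending on the assumed rate and pattern, roughly 6% to 27% of infants would be dropped for sodium and 9% to 27% for weight. All these figures rest on assumed missingness of 3% to 10%; none comes from the documents.

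The cost is mainly precision, and at 48 h the avoidable part is modest: about 1.5% to 5% on the standard error. A reader might infer that objectives 3 and 4 are seriously biased. The simulations do not show this: with one loss rule in both arms the 48 h difference moved from 3.0 to no lower than 2.84, and it reached 2.67 only when loss followed opposite sodium extremes in the two arms. The documents give no evidence of such a pattern. Nor does the point touch the stated hypothesis on hyponatremia, which is analysed as a relative risk. The change is worth making because it is cheap and keeps outcomes that the plan itself defines.

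**What to change.** Replace the choice between repeated measures ANOVA and Kruskal-Wallis for the serial outcomes with one prespecified linear mixed model for repeated measures per outcome (the MIXED procedure in the named SPSS version):

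- Fixed effects for arm, time and arm-by-time, with all observed values from randomised infants, whether or not later values are missing.
- Arm differences in change at the defined time points: 48 and 72 h for sodium; 24, 48 and 72 h for weight.
- Deaths and other losses before 72 h reported by arm beside these results, because values after death do not exist and the model should not be read as supplying them.

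The cost is a few sentences of analysis text and a different procedure in the same software; no extra data are needed. The model assumes that missing values are predictable from observed ones, generally a weaker assumption than the complete-case analysis needs. It cannot inform the change in infants with no value after the initial one, which is a further reason to show losses by arm. Since the rank-based branch is removed, the plan should also say how residuals will be checked and what will be done if they are clearly non-normal.

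### Kruskal-Wallis is named as the non-normal substitute for repeated measures ANOVA, but it cannot test whether the 72-hour course differs between arms

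*Combined protocol and SAP*

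**What the plan says.** All of the relevant text is in the combined protocol and SAP.

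- **Method.** In Study design and statistical analysis, one sentence sets the method for six variables. Change in each of them "will be evaluated using repeated measures ANOVA or Kruskal-Wallis test depending on data distribution". The variables it lists are serum sodium, creatinine, chloride, bicarbonate, glucose and weight. Shapiro-Wilk is the named check of distribution.
- **Repeated data.** The same section: "Blood samples will be taken every 24 hours for 3 days". Weight is also recorded daily for three days.
- **Arm comparison.** The same section: "change of serum sodium and weight change will be evaluated and compared between groups during this time frame (72hrs". This covers sodium and weight.
- **Change defined for two variables only.** Definitions, for sodium: "Change in serum sodium: The difference between serum sodium (at 48 and 72hrs) and initial serum sodium". The entry for weight reads: "Weight change: The difference between weight (at 24, 48 and 72hrs) and birth weight". Creatinine, chloride, bicarbonate and glucose have no definition of change and appear in none of the five objectives.
- **A two-group rank test is already named.** Study design and statistical analysis: "those with abnormal distribution with Mann-Whitney U test or Fisher exact test".

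The plan names no rank method for repeated measures, no mixed model and no transformation. It gives no main time point and does not say how Kruskal-Wallis is to be applied to serial values.

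**The concern.** The sentence treats the two methods as alternatives that answer the same question. Repeated measures ANOVA handles correlation within an infant and can include arm, time and their interaction. Kruskal-Wallis compares independent groups on a single factor. The result of a normality check would therefore decide, variable by variable and after the data are seen, whether the difference in 72-hour course is tested at all.

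At stake are the non-normal branch of objectives 3 (serum sodium) and 4 (weight) and the four chemistry variables. The relative risks of hyponatremia and hypernatremia (objectives 1 and 2) do not pass through this sentence.

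**Working it through.** The plan states no sample size, standard deviation or correlation, so it has no figure to reproduce. The check asks what Kruskal-Wallis does under each way of applying it.

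**1. One change per infant, by arm.** This is valid. With two arms it is the Mann-Whitney test: on one simulated data set, Kruskal-Wallis and asymptotic Mann-Whitney without continuity correction both gave p = 0.1354. Following the definitions, it would run at two times for sodium and three for weight. If the tests were independent, the chance of at least one false positive would be 1 − 0.95² = 9.75% or 1 − 0.95³ = 14.3%. Simulation with correlated times gave 11 to 14% for three.

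**2. Other uses.** Assumed inputs, none from the plan: no true arm effect; 20, 50 or 100 infants per arm; within-infant correlation r = 0.3, 0.5 or 0.7; normal, right-skewed or heavy-tailed data; 10,000 runs per setting. Rejection rates (%) at nominal 5% for 50 per arm, normal data and equal correlation:

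| Use of Kruskal-Wallis | r = 0.3 | r = 0.5 | r = 0.7 | Range over all settings |
|---|---|---|---|---|
| Three daily values stacked by arm | 11.5 | 15.8 | 20.5 | 10–21 |
| Changes stacked by arm, two times | 10.5 | 10.7 | 10.5 | 10–13 |
| Changes stacked by arm, three times | 17.2 | 15.8 | 16.3 | 15–19 |
| Three days compared within one arm | 1.8 | 0.4 | 0.0 | 0–2.4 |
| Change at 72 h by arm, one per infant | 4.8 | 4.8 | 4.9 | 4.3–5.4 |

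The fourth use makes no arm comparison at all.

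**3. Closed-form check.** Stacking m values per infant inflates the variance by V = 1 + (m − 1)r, and the rejection rate is about 2[1 − Φ(1.96/√V)].

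- Three daily values: V = 1 + 2r = 1.6, 2.0, 2.4, giving 12.1, 16.6 and 20.6%.
- Changes sharing one baseline, under equal correlation, correlate (1 − r)/[2(1 − r)] = 0.5 whatever r is. So V = 1.5 for two times (11.0%) and 2.0 for three (16.6%).

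Both agree with the simulation. V depends on correlation, not on sample size.

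**4. How often the branch would be entered.**

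- Six truly normal, independent variables, each tested once at 0.05: 1 − 0.95⁶ = 0.265, about 26% for at least one.
- A mildly right-skewed analyte (assumed log SD 0.3), arms pooled, 40/100/200 infants: about 48/87/99% if Shapiro-Wilk is applied to the measured levels, but about 15/26/40% if applied to the change from the initial value, where much of the skew cancels. The plan does not say which.
- Sodium: log SD 0.3 is implausible. Around an assumed median of 140 mEq/L, the central 95% range would be 140 × e^(±1.96 × 0.3), or 78 to 252 mEq/L; the plan's own cut-offs are 130 and 150. With an assumed log SD of 0.03 to 0.05, rejection is about 4 to 13%, counting both levels and changes.

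**The case against.** The strongest reply is that the invalid uses are hypothetical. For sodium and weight, the only affected variables with an objective, the plan defines a per-infant difference and says it is compared between groups. Read naturally, that is a valid test at each time. Nothing in the plan tells the analyst to stack rows or to ignore the arms. This stands. A reader might infer that the sodium and weight results would carry a 10 to 21% error rate; the text does not support that. Such uses are only left open, and chiefly for the four chemistry variables.

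A reader might also infer from the 48/87/99% figures that most variables would end in this branch. Those figures hold for levels with an assumed skew, not for changes, and not for sodium.

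It can also be said that objectives 3 and 4 ask only to assess change and request no interaction test, and that a Mann-Whitney fallback still gives no joint test of the profile. The second part stands and limits what the fix can achieve. The first does not remove the point: the plan itself chose a repeated-measures method for these variables, and the substitute does not do that job.

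**Conclusion.** The point holds in a limited form. Kruskal-Wallis is the wrong substitute in this sentence, and no other text supplies a repeated-measures method for non-normal data. For sodium and weight, the loss is the joint test of the 72-hour course, together with two or three separate tests and no main time. For the four chemistry variables, the plan does not settle what enters the test, so inflated (about 10 to 21%) or very conservative (0 to 2.4%) uses are not excluded. Those rates rest on assumed correlations of 0.3 to 0.7.

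The frequency of entry into the branch cannot be fixed from the documents. The repeated measures ANOVA branch is not in error, objectives 1 and 2 are unaffected, and no general gain in power is claimed. Severity is minor to moderate. Confidence is high on the mismatch of tests and lower on its practical effect.

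**What to change.** Delete Kruskal-Wallis from the sentence and specify instead:

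- **Model.** For variables that fail normality, a linear mixed model (SPSS MIXED) with arm, time and arm-by-time, after log transformation of clearly right-skewed analytes. The same model may serve the normal branch for consistency.
- **Baseline.** For weight, use birth weight. For sodium and chemistry, use the initial sample as covariate only if it is confirmed to precede allocated sodium. The Introduction says "Infants receive at 24 hours of life; sodium (5mEq/kg/day) versus less than 1mEq/kg/day", while the description of the groups refers to day of life one, and neither shows whether the sample comes first. If it does not, model it as an outcome time without a baseline term.
- **Reporting.** Name one main time in advance, define change for the four chemistry variables, and give the arm difference at each time with a 95% CI.
- **Last resort.** Where normality still fails, use Mann-Whitney on the per-infant change at the named time (on the value itself if the initial sample is not pre-treatment). State that this tests one contrast and not the 72-hour profile.

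The cost is SAP wording and slightly more analysis work, with the same data and software. Log-scale effects are read as ratios. Transformation does not cure heavy tails or left skew, so the rank fallback must stay, and it gives no joint profile test.
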